10.3 Calendar for Observational Cohort

Timepoints	Baseline	Weekly during Concurrent Radiation and Cisplatin	Midpoint (After IMRT)	Endpoint (4-6 weeks following Midpoint testing)	Off-treatment	Off study
Studies:						
Muscle Strength and Endurance Testing	X		X	X		
Body Composition (DXA)	X		X	X		
Plasma/Salivary Nitrate/Nitrite	X		X	X		
QOL and Mucositis	X		X	X		
Ct SCAN (body comp)	X		X	X		

11. MEASUREMENT OF EFFECT

11.1 Toxicity

For the purposes of this study, patients receiving beetroot supplement will be re-evaluated for toxicity as listed above and weekly during radiation as per institutional standard. All subjects receiving beetroot supplement will be evaluated for toxicity from the time of their first treatment with beet root to the end of study. Subjects will also be required to record each dose of beet root juice, including date and time, and subjective side effects (i.e. nausea, diarrhea, allergic reactions) noted after each dose. Subjects receiving only muscle strength testing will not be followed for toxicity as they receive standard of care and supportive medications as per routine. These subjects are not considered to be part of the interventional study but certainly serve as a baseline observational cohort.

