Study volunteers will be asked to retain all used and unused study packaging on a weekly basis to turn in to study staff at the end of the week. Study packaging will be compared to the patient generated compliance log to document weekly compliance data. Subjects who are deemed "non-compliant" with the beetroot protocol (less than 3 consumed supplements during any 1 week period between baseline and midpoint measures) will be excluded in the per protocol analysis. Compliance to beet root consumption between midpoint and endpoint measure will be encouraged with weekly phone calls by nutrition graduate students supervised by [name]. [name] will oversee all aspects of the supplementation protocol. The Investigational Drug Service (IDS) at the University of Kentucky will assist with storage, supply management, quality control, and transfer of all beet root.

Bulleted supplementation administration guidelines for each study period are provided below: Baseline and prior to IMRT enrollment (supplement initiation period):

- Following randomization, participants will be taught to self-administer their supplement by study personnel.

- The CRA or nutrition student will then distribute the supplement needed for the 1-2 weeks prior to IMRT to the participant.
- The supplement powder will be packaged in 10g portions by the IDS. Packaging will only be identified by the letter “A” or “B” and only IDS staff will be unmasked to supplement assignment.
- Participants will begin daily, single dose supplementation (M-F during the afternoon hours) on the first day of receiving their supplement from study personnel.
- Participants will be taught to mix their assigned powder with 120mL of water and self-administer within 30 minutes of mixing.
- Compliance during this time period will be encouraged by phone calls, a supplement “count,” and with a patient generated supplement log sheet.

7-8 week IMRT treatment period (daily supplement observation period):

- Participants will be asked to continue daily (M-F) self-administration of the supplement. The pre-measured supplement powder will be provided to the participant on a weekly basis and patients will be asked to consume the supplement during the afternoon hours (M-F).
- At the beginning of treatment and throughout the IMRT period, study personnel will assess the need to provide additional education on proper self-administration of the study supplement (ex. Transitioning from PO feeding to enteral feeds).

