7.1 Adverse Event List(s) for Concentrated Beet Root

BEET ELITE™ is an oral concentrated beet root dietary supplement and not specifically FDA approved. Since BEET ELITE™ is not a drug, there is no Investigator Brochure. This supplement will be obtained from Neogenis® Labs, Inc., Austin, Texas. The BEET ELITE™ product is made from organic beet root crystals, natural flavors, malic acid, and stevia extract and is manufactured in a GMP certified facility. The concentration of the shot is equivalent to 6 beets in one shot.

Beet Root Toxicities:

Potential adverse effects of beet root are rare and include: stomach cramping/diarrhea, pink coloration of urine and stools, and allergic reactions. These side effects are consistent with events that may occur with normal beet consumption (as a food). There have been no reports of mucosal injury in the head and neck, or irritating effect on the oral mucosa.

Methemoglobinemia has been reported in infants who have consumed high levels of nitrate, but these findings have largely been discredited due to confounding cases of gastroenteritis and co-ingestion of sodium nitrite (from contaminated well water). Methemoglobinemia has not been documented in adults consuming nitrates at the level proposed in this trial. Given the oxalate content of beet root (28), caution should be taken for individuals with a history of nephrolithiasis or gall bladder dysfunction.

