9.4 Diet and nutrition status monitoring

Nutrition intake data will be collected randomly within a two week period at baseline and midpoint and will not be scheduled on CCTS testing days. All nutrition data collection and management procedures will be overseen by [name] in collaboration with the MCC registered dietitian.

Twenty four hour dietary recalls will be collected in-person twice at baseline and midpoint (4 total 24-hr recalls per subject) by a nutrition graduate student trained in dietary assessment. During clinical status checks/chemo visits at the MCC, participants will be asked to report their food and beverage intake (enteral and/or by mouth) over the previous 24-hours. The Nutrition Data System for Research software (NDSR version 2012, Minneapolis, MN) will be used to organize and assess all dietary data collected. NDSR uses the multiple-pass method to help improve the validity of dietary data. This method is a standardized recall strategy that refers to the number of times a participant's food intake is reviewed during the interview in - an effort to improve recall accuracy (10, 11). Enteral feeding regimens during the 7 week IMRT period will also be monitored closely with clinical progress notes and communication with the MCC registered dietitian to document feeding interruptions, change in formula type, volume, and tolerance. Subjects will also provide a daily beet root juice intake diary (Appendices C and D) and side effect profile. A comprehensive summary of nutrient analysis reports will be generated for all participants.

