13.4 Reporting and Exclusions

13.4.1 Evaluation of Toxicity

All subjects on beet root supplementation will be included in the safety analysis, with toxicities graded according to NCI CTCAE v4.0. Incidence tables will be generated to summarize incidence of patients reporting at least one episode of each specific adverse event, incidence of adverse events causing withdrawals and incidence of serious adverse events. Listing of adverse events by patients will include the time to onset, the duration of each event, the severity of each event, and the relationship of the event to study therapy, whether it was a serious event, and whether it caused withdrawal. This will also capture all incidence and severity of mucositis during the duration of this study.

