APPENDIX C

Patient Name: _____
Patient ID#: _____
Date Range: ____/____/____ to ____/____/____

Weekly Supplement Log

Instructions for the participant: This is a weekly log on which you are to record each supplement dose you take. For each dose write down the day, time and amount consumed (only fill out if supplement is mixed with water). Bring the log and all supplement packaging with you to your next scheduled supply pick-up.

Dose Number	Day (Example: Monday)	Time (Example: 12:00pm)	Amount Consumed (percent drank: 50%, 100%)	How was it taken (mouth or tube)
1				
2				
3				
4				
5				

Did you vomit up your supplement within 15 minutes of taking it on any day? If yes, how many days? _____

Did you retake the supplement each time? If yes, how many times did you retake it? _____

Patient Initials: _____

Date: _____

Section to be completed by research personnel:

Distribution Date: ____/____/____

Return Date: ____/____/____

Total Bags Returned: _____

Number of Empty Bags: _____

Comments: _____

Signature (Research Personnel)

Date

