APPENDIX D

Patient Name: _____

Patient ID#: _____

Date Range: ____/____/____ to ____/____/____

Monthly Supplement Log

Instructions for the participant: This is a monthly log on which you are to record each supplement dose you take. For each dose write down the dose number, time and amount consumed as a percent (only write down if supplement is mixed with water) under the day you had it. For example, write down: Dose 1, 12pm and 50% if you drank half of the supplement. Bring the log and all supplement packaging with you to your next scheduled supply pick-up.

Sunday	Monday	Tuesday	Wednesday	Thursday	Friday	Saturday
 Mouth  Tube						
 Mouth  Tube						
 Mouth  Tube						
 Mouth  Tube						
 Mouth  Tube						

Did you vomit up your supplement within 15 minutes of taking it on any day? If so, how many days?

Did you retake the supplement each time? If not, how many times did you retake it? _____

Patient Initials: _____

Date: _____

Section to be completed by research personnel:

Distribution Date: ____/____/____

Return Date: ____/____/____

Total Bags Returned: _____

Number of Empty Bags: _____

Comments: _____

Signature (Research Personnel)

Date

Beetroot Juice Supplement Instruction Sheet (by stomach tube)

1. Mix the supplement powder with 4-8 oz of water only.
2. Do not mix the powder with anything other than water or more than 8 oz of water.
3. You may pour water into a glass and add in the powder or place the powder in a small bottle of water to pour in the tube.
4. Flush the tube with a small amount of water before and after administration of the supplement according to your physician's guidelines.
5. Pour the entire supplement within 2-3 minutes so it is all in the stomach at the same time.
6. On your supplement log write down the day (example: Monday), dose number (example: 1), approximate time you mixed the powder (example: 9:00am), and how much you administered (as a percent, example: 100%).
7. Administer the supplement between afternoon hours of 12-5pm.
8. The supplement is meant to be taken on weekdays (Monday-Friday).
9. If a dose is forgotten, take as soon as you remember that day. Then resume the supplement schedule the next day.

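### Section 11.1 requires side effects to be recorded with each beetroot dose, but the patient logs have no field for them, and on the calendar about 40–50% of the supplement period has no weekly toxicity check

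*Combined protocol and SAP*

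**What the plan says.** All references are to the combined protocol and SAP.

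- **Requirement.** Section 11.1 says: "Subjects will also be required to record each dose of beet root juice, including date and time, and subjective side effects". It names nausea, diarrhea and allergic reactions as examples.
- **Instrument.** Section 9.4 says: "Subjects will also provide a daily beet root juice intake diary (Appendices C and D) and side effect profile".
- **Forms.** The weekly log (Appendix C) has one symptom question: "Did you vomit up your supplement within 15 minutes of taking it on any day? If yes, how many days". The monthly log (Appendix D) has the same one: "Did you vomit up your supplement within 15 minutes of taking it on any day? If so, how many days". Each then asks whether the dose was retaken.
- **Expected effects.** Section 7.1 lists "stomach cramping/diarrhea, pink coloration of urine and stools, and allergic reactions" and calls them rare.
- **Toxicity schedule.** The calendar in 10.2 marks toxicity assessment at Baseline, weekly during radiation, at Midpoint and at Endpoint. Section 11.1 likewise ties the weekly assessment to radiation. Section 5.2 also describes weekly clinic toxicity assessment, covering beetroot-related toxicity, but does not confine it to the radiation weeks.
- **Contact after IMRT.** Section 5.1.3 says: "Compliance to beet root consumption between midpoint and endpoint measure will be encouraged with weekly phone calls". It also provides for log and supplement counts two or more times a month. The stated purpose of both is compliance.
- **Reporting.** Section 13.4.1 promises: "Listing of adverse events by patients will include the time to onset, the duration of each event".

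**The concern.** The plan sets a per-dose recording duty and then gives patients forms on which they cannot carry it out. Toxicity of beetroot given with radiation or chemoradiation is a secondary objective (1.2), and Section 5 presents safety as a purpose of the trial. Stomach cramping, diarrhea and allergic reactions are effects that a patient notices at home and that may be over before the next visit.

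Three features of the design raise the value of prompt recording:

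- The observational cohort is not followed for toxicity (11.1). Apart from the mucositis assessment in 10.3, there is no concurrent adverse-event comparison, so attribution leans on the timing of an event relative to a dose.
- The interim safety consideration in 13.2 looks at treatment completion, not adverse events.
- The Section 6 rules for grade 3–4 events related to beetroot can be applied only if staff learn of an event while dosing continues.

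At stake is the quality of the toxicity estimate and of the onset and duration listing. The primary endpoint, treatment compliance, is not affected.

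**Working it through.** **1. What 11.1 asks for, against what the forms hold**

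| Item | Required by 11.1 or listed in 7.1 | Patient field in Appendix C or D |
|---|---|---|
| Day or dose number, time | 11.1 | Yes |
| Amount, route | – | Yes |
| Vomiting within 15 minutes | – | Yes, as a count of days, without dates |
| Nausea | 11.1 | No |
| Diarrhea, cramping | 11.1 (diarrhea), 7.1 | No |
| Allergic reaction | 11.1, 7.1 | No |
| Pink urine or stool | 7.1 | No |

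The comments line on each log is in the part completed by research staff. The patient instruction sheets ask for day, dose number, time and amount, and do not mention writing down side effects. The only other symptom form appended is the mucositis worksheet. This gap covers 100% of exposure.

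**2. Share of exposure without a weekly check on the calendar**

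The plan gives no figure to reproduce. Inputs:

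- before IMRT: 1–2 weeks, minimum 4 days (5.1.3);
- IMRT: 7 weeks (5.1.3), 7–8 weeks (supplement guidelines within 5.1.3), or 6–7 weeks (5.1.1.1);
- after IMRT: 4–6 weeks (5.1.3).

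Share = (weeks before + weeks after) / (weeks before + IMRT weeks + weeks after), taking Midpoint as the end of IMRT.

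- 7-week IMRT, shortest: (1+4)/(1+7+4) = 5/12 = 41.7%.
- 7-week IMRT, longest: (2+6)/(2+7+6) = 8/15 = 53.3%.
- 8-week IMRT, shortest: (1+4)/(1+8+4) = 5/13 = 38.5%.
- 8-week IMRT, longest: (2+6)/(2+8+6) = 8/16 = 50.0%.
- Lowest over all stated durations: 4 days = 0.571 week, so (0.571+4)/(0.571+8+4) = 4.571/12.571 = 36.4%.
- Highest over all stated durations: (2+6)/(2+6+6) = 8/14 = 57.1%.

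At five doses a week, 5–8 weeks is 25–40 scheduled doses per patient: 25 of 60 to 40 of 75 with 7-week IMRT, and 25 of 65 to 40 of 80 with 8-week IMRT.

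**3. Where that share lies**

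The lead-in of 1–2 weeks runs straight into the weekly on-radiation checks, so recall there is short. The longer interval is Midpoint to Endpoint. With 7-week IMRT and the two pairings above it is 4/12 = 33.3% to 6/15 = 40.0% of exposure. In those 4–6 weeks the calendar has one closing assessment, at Endpoint, and no weekly assessments in between.

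**The case against.** The strongest reply is that toxicity is collected throughout. Section 11.1 evaluates beetroot patients from first dose to end of study, 10.2 follows toxicity to endpoint testing with assessments at Midpoint and Endpoint, and 7.5 sends all adverse events to the case report forms. Serious events have their own expedited route (7.3). This stands. A reader might infer that beetroot effects go largely uncollected outside radiation, or depend on unprompted reports. The documents do not support that: the later assessments are scheduled, and staff see logs and packaging in between. What is missing is recording at the time.

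It can also be said that the side effect profile in 9.4 is separate from the diary, since Appendices C and D are attached to the diary only. That is a fair reading, and the form may exist elsewhere, as may the case report forms and the data management plan mentioned in 13.5. But it is not among the appendices, and the instruction sheets do not send patients to it.

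Section 5.2 could be read as weekly assessment for the whole study. If so, the second gap closes, but then 10.2 and 11.1 are wrong. The passages need reconciling either way. A reader might also take the weekly checks to cover radiation toxicities only; 5.2 rules that out, because it names beetroot-related toxicity as of particular interest.

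A further tempting argument is that the weeks outside radiation are the least confounded by treatment toxicity. No passage says so. Section 5.2 follows patients until toxicities of grade 2 or above resolve, which implies that they may persist, and 5.1.2 allows a cetuximab loading dose before radiation begins.

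Finally, 7.1 calls the effects rare and like those of eating beets. That limits the importance of the point but does not remove the mismatch.

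**Conclusion.** The point holds as two separate gaps. The logs lack the side-effect fields that 11.1 requires, for the whole exposure period. On the calendar reading, about 40–50% of the supplement period has no weekly toxicity check (42–53% with 7-week IMRT, 38–50% with 8-week IMRT, 36–57% at the extremes of the stated durations), chiefly the 4–6 weeks between Midpoint and Endpoint. The percentage describes absent weekly checks only. It is not a share of events lost, and it should not be applied to the missing log fields.

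The consequence is that brief, patient-noticed effects, and the onset and duration promised in 13.4.1, would rest on recall at a scheduled visit. This rests on three assumptions: that 10.2 and 11.1 govern over 5.2, that no side effect profile form is in use beyond the appendices, and that the calls and counts do only what 5.1.3 describes. It is a correctable weakness in a secondary safety objective and does not threaten the trial.

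**What to change.** 1. Add dated side-effect fields to Appendices C and D (nausea, diarrhea or cramping, allergic reaction, other; start and stop), or append the side effect profile form. Add a matching line to both patient instruction sheets.
2. Put the same questions into the phone calls already planned before IMRT and weekly after it. Pass positive answers to the study clinicians for CTCAE grading under the protocol's existing rules.
3. Show these contacts under toxicity assessment in 10.2.
4. Reconcile 5.2 with 10.2 and 11.1 on how often toxicity is assessed outside radiation.

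The cost is two revised forms, a revised instruction line and a short call script, using calls, log reviews and staff already in the plan. No visits are added. The downside is slightly longer calls and more low-grade adverse-event entries.

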11.2 Antitumor Effect – Solid Tumors

Response and progression are not the primary endpoints of this study, however, response and progression will be evaluated in this study using the new international criteria proposed by the revised Response Evaluation Criteria in Solid Tumors (RECIST) guideline (version 1.1) [Eur J Ca 45:228-247, 2009]. Changes in the largest diameter (unidimensional measurement) of the tumor lesions and the shortest diameter in the case of malignant lymph nodes are used in the RECIST criteria.

11.2.1 Definitions

Evaluable for toxicity. All patients will be evaluable for toxicity from the time of their first treatment with beetroot juice/.

Evaluable for objective response. Only those patients who have measurable disease present at baseline, have received at least one cycle of therapy, and have had their disease re-evaluated will be considered evaluable for response. These patients will have their response classified according to the definitions stated below. (Note: Patients who exhibit objective disease progression prior to the end of cycle 1 will also be considered evaluable.)

Evaluable Non-Target Disease Response. Patients who have lesions present at baseline that are evaluable but do not meet the definitions of measurable disease, have received at least one cycle of therapy, and have had their disease re-evaluated will be considered evaluable for non-target disease. The response assessment is based on the presence, absence, or unequivocal progression of the lesions.

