11.2.4.3 Evaluation of Best Overall Response

The best overall response is the best response recorded from the start of the treatment until disease progression/recurrence (taking as reference for progressive disease the smallest measurements recorded since the treatment started). The patient's best response assignment will depend on the achievement of both measurement and confirmation criteria.

For Patients with Measurable Disease (*i.e.*, Target Disease)

Target Lesions	Non-Target Lesions	New Lesions	Overall Response	Best Overall Response when Confirmation is Required*
CR	CR	No	CR	≥4 wks. Confirmation**
CR	Non-CR/Non-PD	No	PR	≥4 wks. Confirmation**
CR	Not evaluated	No	PR	
PR	Non-CR/Non-PD/not evaluated	No	PR	Documented at least once ≥4 wks. from baseline**
SD	Non-CR/Non-PD/not evaluated	No	SD	
PD	Any	Yes or No	PD	no prior SD, PR or CR
Any	PD***	Yes or No	PD	
Any	Any	Yes	PD	

* See RECIST 1.1 manuscript for further details on what is evidence of a new lesion.
 ** Only for non-randomized trials with response as primary endpoint.
 *** In exceptional circumstances, unequivocal progression in non-target lesions may be accepted as disease progression.

Note: Patients with a global deterioration of health status requiring discontinuation of treatment without objective evidence of disease progression at that time should be reported as “*symptomatic deterioration*.” Every effort should be made to document the objective progression even after discontinuation of treatment.

For Patients with Non-Measurable Disease (*i.e.*, Non-Target Disease)

Non-Target Lesions	New Lesions	Overall Response
CR	No	CR
Non-CR/non-PD	No	Non-CR/non-PD*
Not all evaluated	No	not evaluated
Unequivocal PD	Yes or No	PD
Any	Yes	PD

* ‘Non-CR/non-PD’ is preferred over ‘stable disease’ for non-target disease since SD is increasingly used as an endpoint for assessment of efficacy in some trials so to assign this category when no lesions can be measured is not advised

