13. STATISTICAL CONSIDERATIONS

13.1 Study Design/Endpoints

This non-randomized, pilot study plans to enroll 35 total patients with previously untreated squamous cell cancer of the head and neck. As the goal of this study is to obtain preliminary data regarding current standard therapy compliance rates for this patient population at the University of Kentucky Markey Cancer Center and assess feasibility of an additional beet juice supplementation during therapy, the primary objective is to estimate treatment compliance defined as completion of radiation alone or radiation and chemotherapy with beet root supplementation during primary treatment. Treatment compliance is defined in more detail in section 5. Secondary objectives to obtain pilot estimates for cancer specific outcomes such as response rate, adverse events, mucositis rates, and 1 and 2 year locoregional control rates and progression-free rates Additional secondary

measures will include strength measures, CT scans, quality of life surveys, nitrate/nitrite levels, endurance testing, handgrip strength, and Body Composition DXA variables of interest (Bone Mineral Density, Bone Mineral Content, Area, % fat). Beet juice rates of completion will also be estimated to assess feasibility of this product.

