13.2 Sample Size/Accrual Rate

The primary endpoint of this study is treatment compliance, for the chemoradiation strata defined as completion of radiotherapy and 3 cycles of chemotherapy with no treatment delay with published historical rates average around 52.1% (30). For those receiving radiation alone, we predict higher compliance rates closer to 70% as these patients tend to experience less mucositis and adverse events during treatment. We anticipate 60% of patients will receive radiation alone versus 40% receiving chemoradiation. 25 total patients (10 – chemoradiation, 15 – radiation alone) receiving beet root supplementation, will result in 90% confidence intervals around each estimated compliance rate with a maximum widths of +/- 27.75% and 22.85% for chemoradiation and radiation alone respectively. The combined estimate of compliance will still have a 90% confidence interval estimate with a maximum width of +/- 17.7% as previously designed. For the 10 subjects in the observational cohort not receiving beet root supplementation, we will still be able to estimate compliance rates +/- 27.75% and obtain pilot data regarding strength outcomes during standard of care therapy. This design is not powered to compare compliance rates between treatment strata or beet root versus standard of care; instead it allows us to gain preliminary information about these rates with a certain amount of precision as pilot data for a larger, more definitive study. We plan to accrue patients over a 2 year period.

There will be a pre-specified safety consideration after half of the planned enrollment in the beet root supplementation (interim after 13) to verify acceptable treatment completion rates as compared to a published historical rate of 52.1%. Two prior beta distributions (non-informative and null-hypothesis based) will be considered with patient information collected from the first 13 enrolled in beet root arm to calculate the posterior probability that the mean proportion of successful completion is less than or equal to historical rates of 52.17% with corresponding 90% credible intervals. The study team will reconsider continuation of the protocol due to safety and feasibility concerns if either arm has a high probability of experiencing a success rate lower than published rates.

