13.4.2 Evaluation of Outcomes

All patients included in the study will be assessed for treatment compliance, even if there are major protocol treatment deviations or if they are ineligible. All of the patients who met the eligibility criteria (with the possible exception of those who received no study medication) will be included in the intent to treat analysis for the primary completion endpoint as well as all secondary outcomes.

Due to concerns of potential non-compliance of taking all beet supplements over the course of primary treatment, a per protocol analysis will also be performed for all patients that consume at least 3 servings of the required beet supplements per week. Percentage of beet supplements taken will also be reported as part of this subgroup analysis.

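### Section 11.2.1 and Section 13.4.2 set different denominators for the response rate, and the one-cycle condition in 11.2.1 is undefined for radiation-alone patients

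*Combined protocol and SAP*

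**What the plan says.** Response rate enters the plan in Section 13.1: "Secondary objectives to obtain pilot estimates for cancer specific outcomes such as response rate". It is not listed among the secondary objectives in Section 1.2.

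Two sections then say who is counted:

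- Section 11.2.1 requires measurable disease at baseline and adds that such patients must "have received at least one cycle of therapy, and have had their disease re-evaluated will be considered evaluable for response". A note in the same paragraph makes one exception: "Patients who exhibit objective disease progression prior to the end of cycle 1 will also be considered evaluable".
- Section 13.4.2 takes the patients who met the eligibility criteria, allows a possible exception where no study medication was taken, and says that they "will be included in the intent to treat analysis for the primary completion endpoint as well as all secondary outcomes".

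The expected treatment mix is in Section 13.2: "We anticipate 60% of patients will receive radiation alone versus 40% receiving chemoradiation", which gives "25 total patients (10 – chemoradiation, 15 – radiation alone) receiving beet root supplementation".

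On confirmation, Section 11.2.4.3 states: "The patient's best response assignment will depend on the achievement of both measurement and confirmation criteria". A footnote to the table in that section limits confirmation to non-randomized trials in which response is the primary endpoint, and Section 11.2 says that response is not primary here.

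**The concern.** One endpoint has two denominators, and nothing ranks one section above the other or says how a patient with no re-evaluation is classified. Two separate problems follow.

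First, the cycle condition does not fit most of the patients. Section 13.2 uses the word for chemotherapy, and Section 5.1.5 uses it for radiation fractions given with cisplatin. No section defines it for radiation alone. It is also unclear for cetuximab, which Section 5.1.2 describes as a loading dose followed by weekly doses.

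Second, the re-evaluation condition removes patients who die early, withdraw, or are taken off study under Section 5.3 and never rescanned. Response is assessed at 6 to 12 weeks (Section 5.4), so there is time for such losses. If these patients would mostly have been non-responders, leaving them out raises the rate.

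Section 13.2 describes the compliance estimates as pilot data for a larger study, and Section 13.1 describes the cancer outcomes as pilot estimates too. A response rate whose denominator can be chosen after the data are seen is a poor planning figure.

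**Working it through.** **The plan's own precision figures.** These are stated for compliance; none is stated for response. Section 13.3 specifies exact 90% binomial intervals. For x successes in n, the lower limit is the 5% quantile of Beta(x, n − x + 1) and the upper limit is the 95% quantile of Beta(x + 1, n − x). The largest half-width over all x is:

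| n | x at maximum | 90% interval | Half-width | Plan (13.2) |
|---|---|---|---|---|
| 10 | 5 | 22.24% to 77.76% | 27.76 points | 27.75 |
| 15 | 8 | 30.00% to 75.63% | 22.81 points | 22.85 |
| 25 | 12 | 30.51% to 65.86% | 17.67 points | 17.7 |

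The plan's figures reproduce, so the same method is used below.

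**Effect of the cycle condition.** Radiation alone: 60% × 25 = 15 patients. If cycle means chemotherapy only, 25 − 15 = 10 patients remain, and the maximum half-width grows from 17.67 to 27.76 points. The direction of the bias depends on how the two strata respond. For illustration, assume 5 of 10 chemoradiation patients and 12 of 15 radiation-alone patients respond. The restricted rate is 5/10 = 50%, and the all-patient rate is (5 + 12)/25 = 17/25 = 68%. Here the restriction lowers the rate. If the chemoradiation stratum responded better, it would raise it.

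**Effect of the re-evaluation condition.** Let M be the number with measurable disease, u the number never rescanned and r the responders. The evaluable-only rate is r/(M − u). The rate with unscanned patients counted as non-responders is r/M. The gap is r/(M − u) − r/M = [r/(M − u)] × u/M.

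The documents give neither the response rate nor u, so both are assumed. Take M = 25 and round responders to whole patients:

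| Assumed response among evaluable | u | Evaluable-only | All 25 | Gap |
|---|---|---|---|---|
| about 70% | 0 | 18/25 = 72.0% | 18/25 = 72.0% | 0.0 |
| about 70% | 2 | 16/23 = 69.6% | 16/25 = 64.0% | 5.6 |
| about 70% | 5 | 14/20 = 70.0% | 14/25 = 56.0% | 14.0 |
| about 50% | 2 | 12/23 = 52.2% | 12/25 = 48.0% | 4.2 |
| about 50% | 5 | 10/20 = 50.0% | 10/25 = 40.0% | 10.0 |
| about 90% | 2 | 21/23 = 91.3% | 21/25 = 84.0% | 7.3 |
| about 90% | 5 | 18/20 = 90.0% | 18/25 = 72.0% | 18.0 |

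For the case with 14 responders, the exact 90% intervals are 49.2% to 86.0% (14/20) and 37.9% to 73.0% (14/25). They overlap heavily.

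Section 3.1 does not require measurable disease, so M may be below 25. With M = 20 and about 70% response, the gap is 13/18 − 13/20 = 72.2% − 65.0% = 7.2 points for u = 2, and 10/15 − 10/20 = 66.7% − 50.0% = 16.7 points for u = 5.

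**The case against.** The strongest reply is that Section 11.2 reads as general RECIST text and that its loose wording does little harm here. Section 11.2.1 speaks of a cycle of therapy, not of chemotherapy, and asks that it be received, not completed. No section says that radiation-alone patients are excluded. Section 13.3 treats the secondary endpoints as descriptive and exploratory. All of this stands, and it limits the weight of the point. It does not say which denominator applies.

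A reader might infer that Section 11.2.1 drops early failures wholesale. It does not: patients with objective progression before the end of cycle 1 stay in. The protection is partial, because it does not reach early death, withdrawal or the symptomatic deterioration described in Section 11.2.4.3, and because its time limit uses the same undefined cycle.

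A reader might also infer that the confirmation sentence in Section 11.2.4.3 rules out any confirmed response before the 1-year scan. The documents do not support this. The table footnote, read with Section 11.2, means that confirmation is not required. Section 5.4 also provides for repeat studies during follow-up, so a second scan before one year is possible. What remains is a sentence that should be aligned with its own footnote.

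**Conclusion.** The conflict between Sections 11.2.1 and 13.4.2 is real, and the cycle condition has no defined meaning for an expected 15 of 25 beet root patients. It would go too far to say that the response rate is certainly inflated. Leaving out unscanned patients raises the rate only to the extent that they would have counted as non-responders, and the gap is zero if everyone is rescanned. If the cycle condition removes radiation-alone patients whose responses were observed, the direction is open.

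The size cannot be derived from the documents. The figures of 5.6 points with 2 unscanned and 14.0 points with 5 unscanned rest on three assumptions: all 25 have measurable disease, about 70% of evaluable patients respond, and unscanned patients are non-responders. The matter should be settled before analysis. Its reach is limited to one secondary, descriptive endpoint.

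**What to change.** In Section 11.2.1:

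- Set the response denominator as all eligible beet root patients with measurable baseline disease who received any study supplement. Receipt of supplement is the right anchor because Section 13.4.2 allows an exception only for patients without study medication. Supplementation starts 1 to 2 weeks before IMRT (Section 5.1.3), so a start-of-radiotherapy condition would create a new mismatch.
- Count patients who are not re-evaluated as non-responders.
- Delete the condition of at least one cycle of therapy.
- Report the evaluable-only rate as a sensitivity figure, with the number of exclusions and the reason for each.

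In Section 13.4.2, state that the measurable-disease restriction is the one exception to the intent-to-treat rule and applies to response rate only. Target-lesion response cannot be classified without measurable disease.

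Optionally, align the confirmation sentence in Section 11.2.4.3 with its footnote: confirmation is not required, because response is not the primary endpoint.

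The cost is wording only. The reported rate may be a few points lower than the evaluable-only figure.
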